1.0 Research Design

1.1 Purpose/Specific Aims

The short-term goal of this project is to gain insight into specific strategies of VR-based rehabilitation to increase motivation and intensity for persons with PD during a cycling task. **The long-term goal of this study is to determine the essential elements in designing a training circuit for persons with PD to promote mobility and fitness resulting increased activity and participation.** The short-term goals will be achieved through two primary aims that build upon the parent grant (1-2) and further refined through a mechanistic aim about the role of attention in explaining behavior in the VE (3).

We aim to build upon our work in PD and that of others in persons post stroke by using augmented visual feedback and competition to increase exercise intensity and motivation while cycling in a virtual environment.

Aim 1: Determine the effect of visual feedback and competition (self or others) during virtual bicycling on neuromuscular (cycling cadence) and cardiovascular (% max heart rate) intensity

Hypothesis: Competition will produce higher neuromuscular and cardiovascular intensity compared to feedback.

Aim 2: Determine the effect of visual-feedback and competition (self or others) during virtual bicycling on the user experience of motivation & enjoyment (Intrinsic Motivation Inventory: IMI) & perception of exercise intensity (Borg Scale)

Hypotheses: Competition will elicit a higher motivation and enjoyment compared to visual feedback. Competition will result in lower perceived exertion compared to visual feedback.

Aim 3: Determine if attention differs (dwell time percentage) in augmented visual feedback bicycling compared to competition (self or others) virtual bicycling

Hypothesis: Attention will be higher during competition virtual bicycling when compared to augmented bicycling.

A. Objectives (see above)

B. Hypotheses / Research Question(s) (see above)

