1.5 Sample Size Justification

Power analyses- Sample size for **Aim 1**: An a priori power analysis was powered upon preliminary cycling cadence data published from the lab. [15] The power analysis conducted in G*Power, [20] determined that 19 participants would be required to reach a power level of 0.80 (Cohen's D =0.7, moderate effect size). **Aim 2**: An a priori power analysis powered on motivation and enjoyment (Intrinsic Motivation Inventory) [21] with an effect size of 0.75 determined that 16 participants would be required. This effect size was adapted from Cikajilo & Potisk 2019, who investigated a fine motor upper extremity task for persons with PD in a fully-immersive environment. We used their reported average effect size of the different IMI subscales. [22] **Aim 3**: There are no pilot data (collected by our team or published by others) for this aim. An effect size will be calculated from these data to power future studies. Considering all the sample size calculations and accounting for a 20% attrition rate, 24 participants will be required for this study.

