5.4 General Data Protection Regulation (GDPR): NA

5.5 NJ Access to Medical Research Act (Surrogate Consent): NA

6.0 Data Management Plan

6.1 Data Analysis

Power analysis was described under sample calculation

Aim / Dependent variable	Factor(s)	Test
Aim 1 – Exercise Intensity		
Cycling Cadence (baseline-adjusted)	condition (feedback & 2 competition conditions)	Repeated measures ANOVA (Rm-ANOVA)

		Post-hoc paired t-tests with appropriate Bonferroni corrections
Heart Rate (age-adjusted)	condition (feedback & 2 competition conditions)	Rm-ANOVA Post-hoc paired t-tests with appropriate Bonferroni corrections
AIM 2 – User Experience of Exercise		
Rating of Perceived Exertion (RPE)	condition (feedback & 2 competition conditions)	Rm-ANOVA Post-hoc paired t-tests with appropriate Bonferroni corrections
Motivation (custom IMI Scale)		
Interest/Enjoyment Perceived Competence Effort/Importance Value/Usefulness	condition (feedback & 2 competition conditions)	Rm-ANOVA Post-hoc paired t-tests with appropriate Bonferroni corrections
AIM 3 - Attention		
Eye-Tracking Data Dwell Time Percentage	condition (feedback & 2 competition conditions)	Rm-ANOVA Post-hoc paired t-tests with appropriate Bonferroni corrections

Bold = Primary comparison Co-variates (exercise readiness, competitiveness, and physical activity) may be included in an ANCOVA analysis. Analysis is simple to parse individual effects and then explore the moderating effects of the cycling condition. Due to the sample size, we will not attempt to impute for missing measures. Analyses will be carried out with all available data for each one of the planned comparisons.

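### The hypotheses compare competition with feedback, but Section 6.1 names no pairs, divisor or decision rule, and Section 1.5 powers an unadjusted test that Section 6.1 does not plan

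*Combined protocol and SAP*

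**What the plan says.** **Hypotheses (Section 1.1).** Aim 1: "Competition will produce higher neuromuscular and cardiovascular intensity compared to feedback". Aim 2: "Competition will elicit a higher motivation and enjoyment compared to visual feedback" and "Competition will result in lower perceived exertion compared to visual feedback". The Aim 3 attention hypothesis has the same form. None says how the self and other versions of competition should differ.

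**Analysis (Section 6.1).** Every outcome has the same entry: a repeated-measures ANOVA on a condition factor with three levels (feedback and two competition conditions), then post-hoc "paired t-tests with appropriate Bonferroni corrections". The pairs and the divisor are not given. The missing-data text mentions planned comparisons but does not list them. No alpha or sidedness is stated.

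**Sample size (Section 1.5).** For Aim 1 the calculation "determined that 19 participants would be required to reach a power level of 0.80", with "Cohen's D =0.7, moderate effect size". For Aim 2, an effect size of 0.75 gives 16. Allowing for 20% attrition, 24 are to be enrolled. There is no calculation for Aim 3.

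**The concern.** Three parts of the plan do not meet. The hypotheses concern competition v feedback. The analysis is a three-condition omnibus test with an unspecified set of corrected pairs. The sample size appears to rest on a single uncorrected pair.

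Two things are at stake. First, the stated power of 0.80 may not apply to the tests that will be run. Second, with two competition conditions, one may beat feedback significantly while the other does not. Nothing says whether that supports the hypothesis, so the conclusion could be chosen after the results are seen.

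**Working it through.** **Inputs.** From Section 1.5: d = 0.7 with n = 19, effect size 0.75 with n = 16, power 0.80, attrition 20%, 24 enrolled. Assumptions, because the documents are silent: alpha 0.05 two-sided; 0.7 and 0.75 are paired effects (mean difference over the SD of differences) and apply to competition v feedback.

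**Step 1: reproduce the plan's figures.** Paired t-test power uses a noncentral t with n − 1 df and noncentrality d√n.
- d = 0.7, n = 19: noncentrality 0.7 × √19 = 3.05; power 0.823 (n = 18 gives 0.799).
- d = 0.75, n = 16: noncentrality 0.75 × 4 = 3.00; power 0.801.
- 19 / 0.80 = 23.75, rounded up to 24.

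All three stated numbers are recovered. Other settings do not return 19 and 16: one-sided 0.05 gives 15 and 13; a normal approximation 17 and 14; 0.05/2 gives 22 and 20; 0.05/3 gives 25 and 22.

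**Step 2: power for one given competition-v-feedback pair after correction.**

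| Effect, completers | 0.05 | 0.05/2 | 0.05/3 |
|---|---|---|---|
| 0.7, 19 | 0.82 | 0.72 | 0.66 |
| 0.7, 24 | 0.91 | 0.84 | 0.79 |
| 0.75, 16 | 0.80 | 0.69 | 0.62 |
| 0.75, 19 | 0.87 | 0.79 | 0.73 |

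Requiring a significant omnibus F first costs little: at d = 0.7 and 19 completers, 0.660 becomes 0.654. The divisor causes the loss.

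**Step 3: the mixed result.** I simulated the three-pair reading (omnibus F, then each pair at 0.05/3) with 19 completers, equal variances and correlations across conditions, and both competition modes truly at 0.7.
- At least one feedback pair significant: 0.81.
- Both: 0.50.
- Exactly one: 0.81 − 0.50 = 0.31.

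At 24 completers these are 0.91, 0.67 and 0.23 (unrounded 0.907 − 0.674).

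**Step 4: Holm over the two feedback pairs.** The smaller p-value is compared with 0.025; if it passes, the larger is compared with 0.05. A feedback pair rejected at 0.05/3 has p < 0.0167. If it is the smaller p-value, it passes 0.025. If the other p-value is smaller still, that one passes 0.025 and this one passes 0.05. So Holm rejects every feedback pair that the three-pair reading rejects, in any dataset. At 19 completers:
- Both modes at 0.7: at least one 0.87 (v 0.81). A given pair has 0.785, so both = 2 × 0.785 − 0.866 = 0.704 (simulation runs give 0.70 to 0.71, v 0.50).
- One mode at 0.7, the other at 0: at least one 0.73 (v 0.66).
- Modes at 0.7 and 0.35: at least one 0.74 (v 0.66).
- No effect of either mode: at least one 0.047 to 0.048, so the familywise error is held.

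**Step 5: a pooled contrast, for comparison.** For (self + other)/2 − feedback, with correlation 0.5 between the two difference scores, the standardised effect is 0.7/√0.75 = 0.808 if both modes work; power at 19 is 0.915 (0.87 to 0.95 for correlations 0.75 to 0.25). If only one works it is 0.35/√0.75 = 0.404, and power is 0.385.

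**The case against.** **Three pairs is not written down.** This stands. Section 6.1 says only that the correction will be appropriate, and the team may have meant the two feedback pairs alone. A reader might infer that the plan definitely spends alpha on self v other; the text does not establish that. But divisor 2 still gives 0.72 rather than 0.80 at 19 completers, and the mixed-result gap remains.

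**The hypothesis is tested.** A reader might infer that competition v feedback is never tested. That goes too far. On any ordinary reading, two of the pairs are self-competition v feedback and other-competition v feedback, and the Aims name competition against self or others. What is missing is how the two results combine.

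**Power is 0.81 for at least one pair.** True on the three-pair reading with equal effects. If one significant pair is enough and both modes work equally well, the stated 0.80 is met. The plan does not say that one is enough, and the figure falls to 0.66 if only one mode works.

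**Attrition may not happen.** Participants attend one session. If all 24 complete, a given pair has 0.79 even at 0.05/3, so the shortfall nearly disappears. The plan itself allows for 20% loss, however.

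**Self v other has value.** Section 1.9 builds the self condition through deliberate framing, and participants rank all three conditions. That is a good reason to report the comparison. It is not a hypothesis in Section 1.1.

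**Bold type may settle it.** Section 6.1 says bold marks the primary comparison, and the text I worked from does not show bold. The table rows are outcomes, so bold probably marks an outcome rather than a pair; the team should confirm.

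**Conclusion.** The point holds in a limited form. The sample sizes in Section 1.5 match an unadjusted paired t-test, while Section 6.1 requires corrected ones. For a given competition-v-feedback pair at 19 completers, power is 0.72 or 0.66 depending on an unstated divisor, against the stated 0.80. On the three-pair reading, about three trials in ten would give a split result even when both modes work equally, with no rule for reading it.

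This rests on d = 0.7 being a paired effect that applies to competition v feedback, on two-sided alpha of 0.05, and, for the simulated figures, on equal correlations across conditions. The exact match to both 19 and 16 supports the first two in part. It cannot show that the earlier cadence data measured this comparison.

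Two stronger conclusions are not supported. The omnibus F is not the source of the loss; the divisor is. Nor is a single pooled contrast clearly the right test: it gains if both modes work (0.915), but has 0.385 against about 0.65 for the three-pair reading if only one does.

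**What to change.** In Section 6.1:
- Name self-competition v feedback and other-competition v feedback as the planned comparisons for each competition-v-feedback hypothesis, tested by Holm at a familywise two-sided 0.05.
- Report self v other as secondary or descriptive, with an estimate and confidence interval.
- State whether one or both pairs must be significant to support the hypothesis.

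In Section 1.5, state alpha and sidedness, say which comparison the 0.7 describes, and restate power for the adjusted test at 19 and at 24 completers.

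This changes wording only. The cost is that self v other is no longer confirmatory; on the three-pair reading it would have had about 0.65 power at 19 completers if only one mode worked. Holm narrows the shortfall but does not remove it: a given pair has 0.785 at 19 completers if both modes work, and about 0.72 if only one does. If the team wants 0.80 for a given pair whatever the other mode does, the 0.05/2 calculation needs 22 completers, or 22/0.80 = 27.5, so 28 enrolled.

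The pooled contrast is an optional alternative if the team expects both modes to work about equally and accepts the loss if they do not.

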1.2 Research Significance (Briefly describe the following in 500 words or less)

Parkinson's Disease (PD) is a neurodegenerative condition that affects over 10 million individuals worldwide. [1] In addition to pharmacotherapy, intense (cardiovascular and neuromuscular) exercise is recommended for persons with PD. Studies investigating the positive neuroplastic effects of intense exercise in animals [2] have been extended to humans regarding improved brain connectivity and upregulation of brain-derived neurotrophic factor. [3, 4] In addition to neuroplastic effects, exercise has been shown to have positive clinical benefits in reducing PD severity and improving motor and cognitive

[figure not shown]
function in persons with PD. [4-6] Specifically, bicycling has been shown to improve balance and mobility and reduce both motor symptoms, and disease severity for persons with PD. [7-10] In achieving and adhering to the intensity of bicycling required to benefit from the training, factors such as the user experience of exercise, specifically motivation, [11] enjoyment, and perceived exertion need to be considered. This is important as adherence to routine exercise is challenging for persons with PD. [12, 13] One method that may enhance exercise intensity for persons with PD is bicycling augmented with a virtual environment (VE). VEs serve as an interactive context to engage the participant in the exercise task. [14] This is because VEs provide visual feedback and cueing that may drive the intensity of the exercise. Specifically, we have shown that neuromuscular cycling intensity (cadence) was increased with visual feedback in short bouts of bicycling in a VE (see Pilot Data). [15] To maintain engagement for longer bouts, competition may provide an additive effect to visual feedback in the VE.

While motor and cognitive outcomes have been documented for persons with PD interacting with virtual environments, [16, 17] less is known about visual attention of persons with PD during motor tasks in VEs. Though visual attention has been studied in persons with PD, [18] only a few studies have investigated visual attention in VEs. [19] To address this knowledge gap, we will be the first lab to investigate eye movements as a surrogate of attention in persons with PD during virtual reality (VR) bicycling to study a mechanistic explanation for behavioral changes.

The ultimate goal of this research is to improve the well-being of persons with PD by making intense exercise more practical and enjoyable for them. It is significant that we bring inter-disciplinary expertise in understanding virtual environments and the demands of implementing the technology in clinical practice. By developing and validating virtual reality simulations that are enjoyable, motivating, and facilitate intense exercise, we aim to remove barriers associated with exercise for persons with PD and improve activity and participation as well as promote a healthy lifestyle. Being a valuable adjuvant to pharmacotherapy in addressing the motor and nonmotor symptoms of PD, intense exercise measured by neuromusculoskeletal and cardiovascular criteria may ultimately have beneficial therapeutic effects in decreasing disease severity and improving well-being.

1.3 Research Design and Methods

This is a controlled study within subject design. It is a single cohort.

Protocol Title: Enhancing Exercise Intensity, Motivation and Enjoyment for Persons with PD (VCycle-Competition)

Protocol Version Date: v5 1.18.23;

Protocol # - Pro2021001412

A. Research Procedures

After phone screening and in-person consent, participants will complete baseline assessments related to personal factors, clinical ratings of PD, and baseline simulation sickness. Then participants will familiarize themselves with three different bicycling conditions. After familiarization, participants will complete each bicycling condition in a counter-balanced random order. Each condition will last 8 minutes (~24 minutes of exercise total) and will be preceded by a baseline cadence assessment. **For the visual feedback condition**, the cyclist will be instructed to cycle at a target cadence that will turn the road markers blue. **For the competition conditions**, the participant will be instructed to cycle fast enough to pass a virtual cyclist in the simulation that is pedaling at the target cadence. **Measurements** of cardiovascular (HR) and neuromuscular (cycling cadence) intensity and visual attention (eye-tracking data) will be recorded continuously during both cycling conditions. Ratings of perceived exertion (RPE) will be collected at the beginning, midpoint, and end of each condition. At the end of each cycling bout, motivation & enjoyment and simulation sickness will be assessed. Open ended questions about the experience in each condition will conclude the session. **Participant safety** will be carefully monitored. If the intensity of the exercise is too high, the cyclists may overexert themselves risking adverse cardiovascular events. Therefore, different termination criteria will be implemented to ensure the safety of the patient. Participants will also be supervised at all times for safety on the bike. They will also be monitored for signs of cybersickness (dizziness, sweating) and be given an opportunity to stop at any time.

B. Data Points

See outcome table below (*Table 1*).

C. Duration for Study and Each Subject

The study will be conducted over 20 months. Participants will attend one data collection session, lasting approximately three hours.

D. Endpoints

See Section 1.10 for the Data Monitoring timeline

1.4 Preliminary Data

In the parent study, data have already been collected from 22 participants with PD bicycling in a fully-immersive VE using visual feedback. Participants tolerated the HMD well, showing no significant difference in simulation sickness scores post-trial compared to baseline. Participants also reported moderate-high scores for several constructs of the IMI at the end of the 5-minute bout, including interest & enjoyment, perceived competence, and value & usefulness. Participants also bicycled at a moderate-high intensity, indicated by an average % HR Max of >55% and a bicycling cadence that was >30% faster than their comfortable baseline cadences.

There are many parallels between the parent study and this project. In particular, we have demonstrated our ability to recruit, screen, and clinically test persons with PD. Furthermore, we have collected time series of heart rate and bicycling cadence data during exercise for persons with PD.

HRP-503a - TEMPLATE - Interventional Research Protocol 1.1.21

Protocol Title: Enhancing Exercise Intensity, Motivation and Enjoyment for Persons with PD (VCycle-Competition)

Protocol Version Date: v5 1.18.23;

Protocol # - Pro2021001412

1.5 Sample Size Justification

Power analyses- Sample size for **Aim 1**: An a priori power analysis was powered upon preliminary cycling cadence data published from the lab. [15] The power analysis conducted in G*Power, [20] determined that 19 participants would be required to reach a power level of 0.80 (Cohen's D =0.7, moderate effect size). **Aim 2**: An a priori power analysis powered on motivation and enjoyment (Intrinsic Motivation Inventory) [21] with an effect size of 0.75 determined that 16 participants would be required. This effect size was adapted from Cikajilo & Potisk 2019, who investigated a fine motor upper extremity task for persons with PD in a fully-immersive environment. We used their reported average effect size of the different IMI subscales. [22] **Aim 3**: There are no pilot data (collected by our team or published by others) for this aim. An effect size will be calculated from these data to power future studies. Considering all the sample size calculations and accounting for a 20% attrition rate, 24 participants will be required for this study.

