4.3 Number of Subjects

A. Total Number of Subjects

35 participants will be screened. The study is powered to enroll 24 participants allowing for a 20% attrition rate.

B. Total Number of Subjects If Multicenter Study

18 participants will be screened for collection at the NYIT site. At NYIT, 12 of the 24 participants will be enrolled.

C. Feasibility

At Rutgers there are other active research programs in the same department that have been recruiting participants. There is dedicated parking for participants.

At the NYIT site, there is a boxing program for individuals with Parkinson Disease and other active research programs recruiting participants. There is also adequate parking for participants.

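### The 0.80 power in section 1.5 fits a single unadjusted paired test; if the Bonferroni-corrected paired tests in section 6.1 are two-sided, a named Aim 1 pair has power 0.66 to 0.72 at 19 completers

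*Combined protocol and SAP*

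**What the plan says.** Section 1.5 (Sample Size Justification) names G*Power as the software. For Aim 1 it uses Cohen's d = 0.7, a calculation "powered upon preliminary cycling cadence data published from the lab", which "determined that 19 participants would be required to reach a power level of 0.80". For Aim 2, on the Intrinsic Motivation Inventory (IMI), the calculation "with an effect size of 0.75 determined that 16 participants would be required"; no power is given for that one. The section concludes that, "accounting for a 20% attrition rate, 24 participants will be required for this study". Section 4.3 repeats this: "The study is powered to enroll 24 participants allowing for a 20% attrition rate". Neither section gives an alpha, a sidedness, the test behind the calculation or an allowance for multiple comparisons.

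Section 6.1 (Data Analysis) refers back to 1.5 for power. For every outcome it plans a repeated-measures ANOVA over three conditions (visual feedback, competition against self, competition against others), then post-hoc "paired t-tests with appropriate Bonferroni corrections". It does not say how many comparisons the correction covers. It rules out imputation and adds: "Analyses will be carried out with all available data for each one of the planned comparisons". The Aim 1 hypothesis in section 1.1 is directional: competition should give higher intensity than feedback.

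**The concern.** The sample size appears to have been worked out for one paired comparison at the full 0.05, whereas the analysis plan splits alpha over two or three. The three-level omnibus F test has no direction, and it can be significant because the two competition types differ from each other. The directional Aim 1 hypothesis can therefore be shown only by the paired tests, and those are the tests that carry the correction.

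At stake is how a non-significant pair will be read. A reader told that the study has 80% power may take a null result for, say, self-competition versus feedback as good evidence of no effect. If the tests are two-sided and corrected, the chance of missing a true d = 0.7 in a named pair is 28% to 34% at the planned 19 completers.

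**Working it through.** **Inputs.** From 1.5: d = 0.7 with n = 19 and power 0.80 (Aim 1); 0.75 with n = 16 (Aim 2); 20% attrition; 24 enrolled. From 6.1: three conditions, so two competition-feedback pairs, or three pairs if self versus other is included. Assumed because the documents are silent: familywise alpha 0.05 within one outcome, and d as the paired dz (mean difference divided by the SD of the differences).

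**Formula.** A paired t-test on n completers has df = n − 1 and noncentrality dz·√n. Two-sided power with Bonferroni divisor m is P(|T| > t at 1 − 0.05/(2m)), with T noncentral t.

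**Reproducing the plan's figures (two-sided, m = 1).**
- d = 0.7: power 0.799 at n = 18 and 0.823 at n = 19, so 19 are needed.
- d = 0.75: power 0.771 at n = 15 and 0.801 at n = 16, so 16 are needed.
- Attrition: 19/0.8 = 23.75, rounded up to 24.

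All three stated sizes follow from a single unadjusted two-sided paired test.

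**Other readings that could give the same sizes.**
- One-sided 0.05 needs 15 and 13, so it does not fit.
- One-sided 0.05/2 = 0.025 needs 19 (0.823) and 16 (0.801), so it fits equally well.
- A three-level repeated-measures ANOVA at 0.05 with f = d/2 needs 20 and 18 at correlation 0.3, and 15 and 13 at 0.5. On a 0.01 grid between those values, it gives 19 and 16 together only at 0.37, a value that 1.5 does not state.

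**Power under the planned correction, two-sided, one named competition-feedback pair.** For Aim 1 at n = 19 the noncentrality is 0.7 × √19 = 3.05.

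| Completers | Aim 1, m = 2 | Aim 1, m = 3 | Aim 2, m = 2 | Aim 2, m = 3 |
|---|---|---|---|---|
| 19 | 0.724 | 0.660 | 0.787 | 0.730 |
| 22 | 0.800 | 0.746 | 0.856 | 0.811 |
| 24 | 0.841 | 0.794 | 0.890 | 0.853 |

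- Completers needed for 0.80 in Aim 1: 22 (m = 2) or 25 (m = 3). With m = 2, Aim 1 keeps 0.80 if at most 24 − 22 = 2 participants are lost. With m = 3 it is just under 0.80 even if none are.
- Chance of missing a true d = 0.7 in the named pair: 1 − 0.724 = 28% or 1 − 0.660 = 34% at 19; 16% or 21% at 24.
- Detectable dz at 19 completers for power 0.80: 0.76 (m = 2) or 0.81 (m = 3).
- If the omnibus test must also be significant, simulation under compound symmetry puts the 19-completer Aim 1 figures at about 0.69 to 0.71 (m = 2) and 0.65 to 0.66 (m = 3).
- The Aim 2 columns assume no correction across the four IMI subscales. Including the subscales makes the divisor 4 × 2 = 8 or 4 × 3 = 12, and power at 19 becomes 0.58 or 0.51.

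**What is not short (Aim 1, 19 completers, both competition types at d = 0.7, compound symmetry).** The omnibus test has power 0.87. The chance of at least one significant competition-feedback pair is 0.87 (m = 2) or 0.82 (m = 3). The chance that both pairs are significant is 0.58 or 0.50, rising to 0.74 or 0.67 at 24.

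**The case against.** The strongest reply is that the plan may already be consistent. The Aim 1 hypothesis is directional, and one-sided 0.05 with Bonferroni over the two competition-feedback pairs gives exactly 19 and 16. The documents call no test two-sided, just as they call none one-sided. This stands, and it makes the shortfall conditional on two-sided tests. It does not remove the need to say which was meant, because readings with different power fit the same sizes. One-sided tests with divisor 3 would still give only 0.77 for Aim 1 at 19.

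Second, section 1.1 singles out neither self nor other competition, 6.1 calls the paired tests post-hoc, and the omnibus and at-least-one-pair figures exceed 0.80. This also stands, and it confines the point to conclusions about a named pair or about both pairs. The bold type that 6.1 uses to mark the primary comparison is not visible in the text available, so nothing here depends on which comparison is primary.

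Third, the gap depends on attrition in a study with one session of about three hours. With all 24 completing it is absent under divisor 2 and negligible under divisor 3. That is fair, but 19 completers is the plan's own planning case.

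A reader might also infer that d = 0.7 measures the effect of visual feedback and so does not apply to competition minus feedback. The documents do not support that. Section 1.5 cites the lab's earlier cadence data without saying which cue, group or contrast gave the value. All that can be said is that the contrast behind d = 0.7 is not stated.

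**Conclusion.** The point holds in conditional form. The stated 0.80 matches one unadjusted two-sided paired test, which is not the corrected set planned in 6.1. On the conventional two-sided reading, power for a named Aim 1 competition-feedback pair at 19 completers falls below the stated 0.80 by about 0.08 (divisor 2) or 0.14 (divisor 3). This rests on d being the paired dz, a familywise alpha of 0.05, and correction within the cadence outcome only.

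A reader might go further and conclude that the trial is underpowered or must enrol more. The documents do not support that: one permissible reading has no shortfall, the omnibus test is adequately powered if both competition types have the assumed effect, and 22 or more completers restore 0.80 under divisor 2. What needs correcting is the power statement and the undefined divisor.

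**What to change.** **Section 6.1.** Set the Bonferroni divisor. Use 2 if the formal tests are the two competition-feedback pairs that carry the hypothesis, with self versus other exploratory. Use 3 if self versus other is to be tested formally.

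**Section 1.5.** State the alpha, sidedness and test behind 19 and 16, and that d is the paired dz. If the tests are two-sided, restate Aim 1 per-pair power over 19 to 24 completers as 0.72 to 0.84 (divisor 2) or 0.66 to 0.79 (divisor 3), or give the detectable dz at 19 completers (0.76 or 0.81). For Aim 2, give 0.79 to 0.89 (divisor 2) or 0.73 to 0.85 (divisor 3) only with the explicit assumption of no correction across the four IMI subscales. At most, add that the contrast behind d = 0.7 is not stated.

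**If one-sided tests with divisor 2 were intended,** say so in both sections; 19 and 16 then stand.

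**Cost.** A few sentences in 1.5 and one number in 6.1, with no added enrolment and no change to procedures. The two-sided restatement is less favourable than 0.80 at 19 completers, and divisor 2 gives up a formal self-versus-other test.
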